## 5. Objectives

The overall goal of this project is to assess the impact of two health care worker interventions designed to improve the mental health and well-being of health care workers in Zambézia Province, Mozambique.

Our specific objectives are as follows:

**Objective 1: Evaluate the impact of resilience training only, anti-stigma training only, and resilience and anti-stigma training (vs. standard of care) on hypothesized mechanisms of behavior change among health care workers through a pilot cluster randomized controlled trial (RCT).**

*Hypothesis 1: We hypothesize that health care workers who participate in this training will report a significant reduction in stigmatizing attitudes towards their patients, increased resilience, decreased emotional exhaustion, and decreased depersonalization of their patients.*

**Objective 2: Investigate the impact of health care worker training to reduce stigma and increase wellness and resilience on patient adherence to HIV treatment and satisfaction with health services.**

*Hypothesis 2: We hypothesize that patients receiving care at the site randomized to both resilience and anti-stigma training will have increased adherence to medication (as determined by proportion of time on medication and self-report) at 6 months, higher rates of viral suppression at 6 months, and increased satisfaction at 6 months.*

**Objective 3: Assess experience of moral trauma depression, anxiety and suicidal ideation among health care workers, and explore the perspectives of services/ interventions that could support those at risk of or experiencing moral trauma.**

*Hypothesis: We hypothesize that understanding the experiences and suggestions on mitigating will support development or improvement of interventions that increase wellbeing of health care workers. We will also capture baseline moral injury among health care workers as well as depression, anxiety, and suicidal ideation among health care workers at 10-11 months post intervention.*

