People living with HIV (survey): The study team will recruit participants to complete the baseline and endline surveys at the time the individuals are leaving an appointment for HIV care at one of four eligible health care facilities. Recruitment will be done using convenience sampling when the individual exits the health facility after receiving care. If the individual is interested in participating in the study, a study assistant will bring them into a private room to discuss their eligibility and study procedures (complete surveys at study baseline or endline, i.e., 6 months after the study begins, and to the use of a subset of data from their medical records regarding ART medication pick-up history within the previous 6 months). If eligible and they agree to participate, their informed consent will be obtained by the study assistant at the health facility. Participants can withdraw at any time without impact on the clinical care they are receiving.

People living with HIV who are followed as part of routine care (estimated n=16,000): The study team will not formally recruit and consent these individuals to participate in the study, as only a chart review will be performed. For the inclusion of these individuals' data, we will seek a waiver of informed consent, to be developed and included in the submission to the ethics committees/Institutional Review Board (IRB), to access their retention data and viral load results over the course of the study.

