## **Procedures for Patients living with HIV**

### *Procedures for PLHIV who have agreed to participate in the survey.*

Survey administration with PLHIV participants enrolled in the study will be completed at two time points: one at baseline (i.e., study initiation) and one at endline (i.e., at 6-7 months after study initiation), including sociodemographic data and three questionnaire components related to: Medical Mistrust, Patient Satisfaction, and Perceived stigma from Health care Providers (**Appendix 2**). The survey will be done at the health facility or at a location suggested by the participant as per the participant's preference, at a location where privacy can be guaranteed as much as possible with the support from a surveyor who is fluent in Echuabo (local language). Participants may be recruited for more than one survey time point, however, different PLHIV participants can be recruited at the two time points. Participants will be requested to allow the use of the Moral Trauma Protocol, Version 1.3; PI: [name], 27 September 2024

of a subset of data related to their ART medication pick-up history for the past 6 months will be collected from their medical records for use in analyzing the survey data (**Appendix 10**). These data will be extracted from the electronic patient tracking system OpenMRS™, which stores clinical information from the medical records of PLHIV registered at the health facility.

*Procedures for PLHIV for whom we will collect routine clinical data.*

We intend to collect demographic and clinical data from patients' medical records that include, but are not limited to: HF, NID, age, sex, level of education, marital status at enrollment in HIV care, date of enrollment in HIV care, date of ART initiation, ARV, Body mass index (BMI), CD4+ T-cell count, HIV-1 viral load (VL) (data and value), WHO clinical stage at the first visit and ART initiation, hemoglobin and full blood count on the date of enrollment in HIV care (or nearest), residence (urban or rural), and records of ART pick-ups (to assess retention) (**Appendix 9**). Data will be extracted from the electronic patient tracking system OpenMRS, that stores clinical information from the medical records of PLHIV registered at the health facility.

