#### **Objective 2:**

With Objective 2 most of our outcomes are continuous measurements, and analyses will be similar to those described above: linear mixed effects models that take advantage of the factorial nature of outcome, with clusters defined as study sites, and unadjusted and adjusted for a small number of PLHIV-level covariates (age, sex, educational level, marital status, language, duration on ART, and history of ART medication pick-ups within the previous 6 months). For binary outcomes (e.g., undetectable viral load), we will fit generalized linear mixed effects models with a logit link function.

Every patient is given 30, 60, 90, or 180 days to pick up their ART medication, as indicated in the medical charts. If a patient picks up medication after the indicated/scheduled date, they will be considered "non-adherent" for each day after their specific pick-up date; this will be assessed over the course of the 6-month follow-up and will be treated as a continuous variable (a proportion between 0 and 1 for each participant). Participants who are lost to follow-up from the health facility during the 6-month follow-up period will be considered "non-adherent" for the days that they are lost. For persons who die or are known to have transferred care outside of the catchment area, the proportion of time on medication will be computed using only time prior to death or transfer of care. For our primary retention outcome (proportion of time on medication), normality assumptions are unlikely to hold, perhaps even after data transformation. Hence, we will fit a cumulative probability model (CPM) with fixed effects for the clinics. The CPM is well-suited for this setting because it does not require symmetry/normality in the outcome (which is bounded between 0 and 1 and likely not normal); in the absence of covariates, it reduces to the Wilcoxon rank sum test. The CPM has been shown to perform well in settings investigating medication adherence. Specifically, the distribution of the proportion of time on medication will be modeled as

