## 15. Timeline

Time (month)	Activities/Description
Month 1	Recruit health care workers from four health facilities (n=100).

Month 1	Among HCW , assess baseline measures of (1) Resilience (2) Stigma (3) Burnout (4) Depersonalization (5) Moral Injury Questionnaire		
Months 1-4	Resilience/Wellness Intervention arm sessions; held bi-monthly	Resilience/Wellness and anti-stigma arm sessions, held bi-monthly	Anti-stigma arm intervention only sessions; held bi-monthly
Months 1-2 & Months 6-7	Recruit a sub-group of PLHIV patients receiving any HIV care and treatment into the study at the four study sites (total n=320) to assess impact of the interventions on medical mistrust, patient satisfaction, and perceived stigma from health care providers via baseline (study start) and end-line (approximately 6 months after study start) surveys.		
Months 1-12	Collect routine clinical data (retention, viral load) from all patients enrolled in care and treatment at the four study sites (n estimated approximately to be 16,000).		
Months 5-7	Among HCW , collect post-intervention surveys (repeat same measures as used at baseline, except for #5 Moral Injury Questionnaire) at all sites (control and intervention).		
Months 8-9	Recruit a sub-group of HCW participants at the three intervention sites for in-depth interviews related to moral injury/ moral trauma.		
Months 8-14	Conduct data analysis of survey outcomes among PLHIV and HCW.		
Months 10-11	Conduct surveys to assess depression, anxiety, and suicidality		
Months 12-15	Conduct data analysis of clinical outcomes among PLHIV.		
Months 12-18	Disseminate findings via community meetings with community members and clinicians		

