## Appendix 9: Routinely collected clinical data of all PLHIV to be extracted from EPTS (Objective 2)

1. Age
2. Sex
3. Date of HIV diagnosis
4. Education level (highest completed)
5. Marital status
6. Number of children alive
7. HIV status disclosed to family (yes/no)
8. ART initiation date
9. ART pick up dates (all during study period)
10. Scheduled ART pick up dates (all during study period)
11. Clinical appointment dates (all during study period)
12. Scheduled clinical appointment dates (all during study period)
13. Viral Load test results and dates (all during study period)
14. Pregnancy status at time of study.
15. Differentiated model of care (all documented during study period)
16. Type of drug dispensation (all documented during study period)
17. Blood pressure (all results during study period)
18. Weight (all results during study period)
19. Height
20. TB treatment
21. WHO staging
22. patient ID
23. CD4 results and dates (all during study period)

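### The viral suppression model has no pre-training viral status, so chance site differences carry into the estimate; the viral load extraction window also needs reconciling

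*Combined protocol and SAP*

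**What the plan says.** The extraction list for all patients, Appendix 9 item 13, reads "Viral Load test results and dates (all during study period". The waiver request in Section 7e has the same scope: "to access their retention data and viral load results over the course of the study". The Timeline (Section 15) places the task "Collect routine clinical data (retention, viral load) from all patients enrolled in care and treatment at the four study sites" in Months 1-12. Training runs in Months 1-4, so the two begin in the same month.

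Section 8 (procedures for patients whose routine data are collected) differs. It cites Appendix 9, yet lists "HIV-1 viral load (VL) (data and value" with no time limit, within a list of "clinical data from patients' medical records that include, but are not limited to" the named items.

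Hypothesis 2 (Section 5) is framed as a level: "higher rates of viral suppression at 6 months". Section 8b likewise defines the outcome as the latest viral load after enrolment, and places it within the primary measure of effectiveness for patients. Section 10, Objective 2, says: "For binary outcomes (e.g., undetectable viral load), we will fit generalized linear mixed effects models with a logit link function". The covariates named there are age, sex, education, marital status, language, time on ART and recent pick-up history. Earlier viral load is not among them.

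**The concern.** Patients enter the cohort already active in care, so some will have an earlier viral load in the same database. Prior viral status is likely to be a strong predictor of the next result. The plan neither clearly extracts it nor uses it.

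The health care worker outcomes are handled differently. Section 10, Objective 1, defines them as changes from baseline, and the adjusted models include the baseline measure.

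The gap matters more here because there is one facility per arm and each factor is tested by setting two sites against two. Randomising four facilities cannot be relied on to balance suppression. If the two trained sites started higher, training looks better than it is; if they started lower, a real effect is masked. The reader of the results would have no table showing which had happened.

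**Working it through.** **1. The plan's own figure.** Section 7c gives no power figure for suppression. For Objective 2 in general it states a detectable difference of 0.64 SD at about 80% power, with m = 4,000 per site, ICC 0.05 and two-sided 5% error. For two sites against two, the normal approximation is:

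(1.960 + 0.842) × √[(1 + (m − 1) × ICC) / m]

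- ICC 0.05: 2.802 × √(200.95 / 4,000) = 0.628 (stated 0.64)
- ICC 0.025: 0.445 (stated 0.45)
- ICC 0.10: 0.887 (stated 0.91)

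Power at the three stated differences is 81.5%, 80.8% and 82.0% respectively. The figures reproduce closely, which confirms the two-against-two contrast.

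**2. How large a chance gap is ordinary.** With two sites per side, site effects alone give the contrast a variance of ICC × (1/2 + 1/2), so its SD is √ICC in outcome-SD units. For a proportion p, multiply by √[p(1 − p)]. This assumes that the plan's ICC range applies to suppression and takes p as 80% or 90%; the documents give neither.

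| ICC | SD of contrast (outcome SD) | At 90% suppressed | At 80% suppressed |
|---|---|---|---|
| 0.025 | 0.158 | 4.7 points | 6.3 points |
| 0.05 | 0.224 | 6.7 points | 8.9 points |
| 0.10 | 0.316 | 9.5 points | 12.6 points |

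At ICC 0.05, simulation puts the probability of a chance gap above 5 points at about 0.44 (90% suppressed) to 0.57 (80%). A 5-point gap between the pair averages is therefore unremarkable under the plan's own ICC.

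**3. How much of the gap reaches the follow-up comparison.** With no training effect and the same persistence at every site:

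false difference = gap in pair averages × [P(suppressed | previously suppressed) − P(suppressed | previously unsuppressed)]

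The assumed persistence rates are 93-96% and 40-60%, so the bracket runs from 0.93 − 0.60 = 0.33 to 0.96 − 0.40 = 0.56.

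- 5-point gap between the two-site averages: 0.05 × 0.33 = 0.0165 to 0.05 × 0.56 = 0.028, or about 1.7-2.8 points.
- 5-point difference at one site only: the pair average moves by 2.5 points, so 0.025 × 0.33 = 0.008 to 0.025 × 0.56 = 0.014, or about 0.8-1.4 points.
- 10-point gap between the two-site averages: 3.3-5.6 points.

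**4. What a baseline value could gain.** If the site-level correlation between prior and follow-up status is r (not given in the documents), the detectable difference at ICC 0.05 becomes 2.802 × √[0.05 × (1 − r²) + 0.95 / 4,000]. That is 0.63 SD at r = 0, 0.54 at r = 0.5 and 0.45 at r = 0.7. This illustration ignores the degrees of freedom lost with four sites.

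**The case against.** Several points on the other side are fair.

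- **The data may be obtainable.** Section 8's list is undated and open-ended, and Section 10 says routine records are not destroyed. A reader of Appendix 9 alone might infer that pre-training viral status is unavailable for every patient. The documents do not support that. Appendix 10 takes the previous 6 months of viral load for survey participants, and some Month 1 tests may precede the first session. These sources help little, however. The survey group is a convenience sample of about 80 per facility, and endline respondents may be different people whose previous 6 months fall largely within the study. Even if earlier results were extracted, no planned model uses them.
- **Sites are randomised.** The imbalance is therefore chance with no fixed direction, and it is wrong to infer systematic bias in favour of training. The site random effect is meant to carry this variation into the standard error. That stands, but it does not take the gap out of the point estimate, and a variance from four sites is poorly estimated.
- **Pick-up history is a covariate and may stand in for viral status.** This is plausible in principle, but Appendix 9 items 9-10 also limit pick-up dates to the study period, so the full-cohort extraction does not clearly supply it.
- **The shorter covariate list in Section 10.** The age, sex and education examples belong to the time-on-medication model and should not be read as governing suppression.
- **Scale.** If 0.64 SD applied to suppression at 90%, it would be 0.64 × 0.30 = 0.19, or about 19 points. Against that, 1.7-2.8 points is small. The plan also admits in Sections 8a and 12 that four sites is a limitation. Both points stand, and they make this an improvement and not a fundamental fault.

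**Conclusion.** The point holds in a limited form. Appendix 9 and the waiver text restrict full-cohort viral load to the study period while Section 8 does not, and they must be reconciled. The suppression analysis has no planned pre-training viral status, so chance site differences carry into the estimate in either direction. The size is about 1.7-2.8 points for a 5-point gap between two-site averages, or 0.8-1.4 for a 5-point difference at one site. It rests on the assumed persistence rates, on those rates being equal across sites, and on no other covariate absorbing the gap.

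A reader might infer that adjusting for prior status would remove the problem. It would do so only if prior status were fully recorded and persistence were the same everywhere. Otherwise it reduces the imbalance and leaves some behind. This is a cheap improvement, useful also because Section 12 says the data are to inform a larger trial, for which suppression by site before training is a direct design input.

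**What to change.** 1. Extend Appendix 9 item 13 to the last viral load result and date in a stated window before study start (for example 12 months), and bring the Section 8 list into line.
2. Widen the waiver wording in Section 7e to cover the same window.
3. Tabulate pre-study suppression by site.
4. Add last pre-study status (suppressed, unsuppressed, none recorded) as a covariate in the suppression model in Section 10, Objective 2.

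The cost is a wider date range on a field already being extracted, one covariate and a change to the ethics wording, which may need an amendment because it covers about 16,000 patients without individual consent. The documents do not state how often viral load is tested, so the size of the none-recorded group is unknown. If it differs by site, some imbalance will remain, so its size should be shown by site in the same table.

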## Appendix 10: Clinical data to be extracted from EPTS for only the PLHIV participating in the survey (Objective 2)

1. Patient ID
2. Date of enrollment in HIV services
3. ART initiation date
4. ART pick up dates (all in previous 6 months)
5. Scheduled ART pick up dates (all in previous 6 months)
6. Differentiated model of care (all in previous 6 months)
7. Viral Load test results and dates (all in previous 6 months)
8. Type of drug dispensation (all documented in previous 6 months)
